Background medication: The continuing SSRI/SNRI dose should have been optimized up to the maximum tolerated dose during Study TRD3013 as per the respective Summary of Product Characteristics (SmPC; or local equivalent, if applicable). During the long-term extension study, a stable dose should be maintained; however, dose modifications to the continuing SSRI/SNRI may be made, if necessary, at the investigator's discretion. Additionally, during the long-term extension study, the SSRI/SNRI may be switched for individual participants by the investigator for tolerability issues. The newly prescribed SSRI/SNRI must be labeled for treatment of depression/MDD in their country of participation and the dosage being taken should be according to the respective SmPC (or local equivalent, if applicable). Off-label use of an SSRI/SNRI is

not permitted. The switch of a participant's SSRI/SNRI should occur at an "every 4 week visit" so that clinician-rated scales and patient-reported outcomes (PROs) are captured prior to the switch; the reason for the switch must be documented in the electronic case report form. If the SSRI/SNRI is discontinued at any time during the study, the esketamine nasal spray must also be discontinued and the participant will be withdrawn from the study.

Study participation will continue for up to a maximum of 2 years (104 weeks), or until esketamine nasal spray becomes accessible in the participant's local country, whichever occurs first.

EFFICACY EVALUATIONS

Efficacy will be assessed using clinician-rated scales (MADRS and CGI-S) and PROs (PH-9 and EQ-5D-5L). The MADRS will be performed by a qualified rater who has sufficient qualifications as documented by experience or training. If possible, for individual participants, the independent rater from Study TRD3013 may continue performing the MADRS in this study. To avoid interrater variability, all efforts should be made to have the same rater rating the same study participants as much as possible.

SAFETY EVALUATIONS

Safety assessments include the monitoring of adverse events, measurement of body weight, vital sign measurements, clinical laboratory tests, and pregnancy testing. Suicide risk will also be assessed throughout the study using the C-SSRS.

STATISTICAL METHODS

As no hypothesis is specified for this study, no sample size estimation is performed. Sample size will be driven by pragmatic considerations. It is expected that 100 to 200 participants will be enrolled in this study.

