1.3. Schedule of Activities (SoA)

			Long-term I	Extension Phase		
		ESK Dosing:			Week 104/	
		Once Weekly			End-of-Study b,c,d/	
		or Every	Every	Every	Early Study	Safety follow-up
	Day 1 ^a	2 Weeks	4 Weeks	24 Weeks	Withdrawal Visite	visit ^f
Visit Window (Days)	+14	±3	±3	±3	±3	±2
Administrative Procedures						
Informed consent	Xg					
Inclusion/exclusion criteria	X					
Patient-reported outcomesh						
PHQ-9			X		X	
EQ-5D-5L			X		X	
Clinician-rated scales and questionnairesi						
MADRS: efficacy assessment			\mathbf{X}^{j}		X	
CGI-S			X		X	
C-SSRS (Since Last Visit version)			X		X	
Safety assessments						
Hematology/chemistry, urinalysis (local)k				X	X	X
Pregnancy testing ¹			X		X	X
Body weight					X	
Nasal examination predose ^m	X	X			X ⁿ	
Vital signs predose ^o	X	X			X ⁿ	
Vital signs postdose ^{o,p}	X	X			X ⁿ	
Vital signs ^{o,q}					Xr	X
Study intervention procedures						
Nasal treatment sessions ^{s,t}	X	X ^u			X ^c	
Drug accountability: esketamine	X	X			X ^c	
Medication compliance counseling (SSRI/SNRI) ^v	X	X				
Ongoing						
Concomitant therapy/psychotherapy	X	X			X	X
Adverse events	X	X			X	X

Abbreviations: C-SSRS=Columbia-Suicide Severity Rating Scale; CGI-S= Clinical Global Impression – Severity; eCRF=electronic case report form; EQ-5D-5L=European Quality of Life Group, 5 dimension, 5-level (questionnaire); MADRS=Montgomery-Asberg Depression Rating Scale; MDD=major depressive disorder; PHQ-9=Patient Health Questionnaire – 9; PRO=patient-reported outcome; SmPC=Summary of Product Characteristics; SNRI=serotonin-norepinephrine reuptake inhibitor; SSRI=selective serotonin reuptake inhibitor.

- Day 1 **should** be the same day as Week 32 visit from Study TRD3013. If a participant cannot receive the esketamine nasal spray dose on the same day as the Week 32 visit in Study TRD3013, the participant may be enrolled in this study (TRD4010) as long as they continue their current SSRI/SNRI and receive their first dose of esketamine nasal spray within 14 days of the Study TRD3013 Week 32 visit date; Day 1 of this study will be the day of the esketamine nasal spray dose. The sponsor will use the PROs, clinician-rated scales, and safety assessments, including clinical laboratory tests, from Week 32 in Study TRD3013 in the database for Day 1 in this study; these procedures do not need to be repeated for participants who return for esketamine nasal spray dosing within 14 days after the Week 32 visit in TRD3013.

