Study participation will continue for up to a maximum of 2 years (104 weeks), or until esketamine nasal spray becomes accessible in the participant's local country, whichever occurs first. Participants will have access to esketamine nasal spray for a maximum of 2 years during this study. If esketamine nasal spray becomes accessible locally before the 2-year endpoint, then participants will be considered as having completed the open-label extension study and will be switched to a commercially available supply if in the opinion of the treating physician, the participant continues to benefit from treatment and the participant wishes to continue the esketamine nasal spray treatment. Once esketamine nasal spray becomes accessible in any given country, all participants in the long-term extension study will be discontinued at all sites in that country. Study site personnel will notify participants of study termination and schedule an end-of-study visit with each participant.

A diagram of the study design is provided in Section 1.2, Schema (Figure 1).

Day 1 Through Week 104

Efficacy will be assessed using clinician-rated scales (MADRS and CGI-S) and patient-reported outcomes (PROs) (PH-9 and EQ-5D-5L). The MADRS will be performed by a qualified rater who has sufficient qualifications as documented by experience or training. If possible, for individual participants, the independent rater from Study TRD3013 may continue performing the MADRS in

this study. To avoid interrater variability, all efforts should be made to have the same rater rating the same study participants as much as possible.

All visit-specific PRO assessments (PHQ-9 and EQ-5D-5L) should be conducted/completed before clinician-rated assessments, any tests, procedures, other consultations, or esketamine nasal spray administration to prevent influencing participant perceptions.

All clinician-rated scales, the MADRS and C-SSRS, must be completed before the nasal treatment session at each visit. Esketamine nasal spray dosing and related safety-monitoring procedures MUST be performed LAST at all visits.

Safety assessments include the monitoring of AEs, measurement of body weight, vital sign measurements, clinical laboratory tests, and pregnancy testing. Suicide risk will also be assessed throughout the study using the C-SSRS.

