5.1. Inclusion Criteria

Each potential participant must satisfy all of the following criteria to be enrolled in the study:

- 1. completed the maintenance phase (Week 32) of Study TRD3013 and had esketamine nasal spray in combination with continuing SSRI/SNRI administered through Week 30 (every 2 week dosing) or Week 31 (once weekly dosing) of Study TRD3013, and continues to be willing to be treated with esketamine nasal spray.
- 2. must, in the opinion of the investigator, be benefiting from continuation of esketamine nasal spray in combination with their current SSRI/SNRI based on efficacy and tolerability assessed on Day 1 of this study.
- 3. must be medically stable based on the investigator's judgment.
- 4. must sign an ICF indicating that he or she understands the purpose of, and procedures required for, the study and is willing to participate in the study.
- 5. a woman of childbearing potential must have a negative urine pregnancy test on Day 1.
- 6. a woman must be (as defined in Appendix 2, Contraceptive and Barrier Guidance)
 - a. Not of childbearing potential
 - b. Of childbearing potential and
 - Practicing a highly effective, preferably user-independent method of contraception (failure rate of <1% per year when used consistently and correctly) and agrees to remain on a highly effective method while receiving study intervention and until at least 6 weeks after last dose the end of relevant systemic exposure. The investigator should evaluate the potential for contraceptive method failure (eg, noncompliance, recently initiated) in relationship to the first dose of study intervention. Examples of highly effective methods of contraception are located in Appendix 2, Contraceptive and Barrier.
- 7. male participants who are sexually active with a woman of childbearing potential must agree to the following during the intervention period and for at least 1 spermatogenesis cycle (defined as approximately 90 days) after receiving the last dose of study intervention (ie, esketamine nasal spray), must fulfill the following criteria:
 - must be practicing a highly effective method of contraception with his female partner.
 - must use a condom if his partner is pregnant.
 - must agree not to donate sperm.

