5.5. Criteria for Temporarily Delaying Enrollment or Administration of Study Intervention

If a participant cannot receive the esketamine nasal spray dose on the same day as the Week 32 visit in Study TRD3013, the participant may be enrolled in this study (TRD4010) as long as they continue their current SSRI/SNRI and receive their first dose of esketamine nasal spray within 14 days after the Week 32 visit date in Study TRD3013; Day 1 of this study will be the day of the esketamine nasal spray dose.

Administration of study intervention may be delayed if the participant has nasal congestion on the dosing day as described in Section 6.1.1, Esketamine Nasal Spray, or if the participant requires adjustment of blood pressure medication.

Appendix 4 provides guidance related to study conduct during the Coronavirus Disease 2019 (COVID-19) pandemic.

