8. STUDY ASSESSMENTS AND PROCEDURES

Overview

The Schedule of Activities (Section 1.2) summarizes the frequency and timing of efficacy and safety measurements applicable to this study.

Visit-specific PRO assessments should be conducted/completed before clinician-rated assessments, any tests, procedures, other consultations, or administration of esketamine nasal spray to prevent influencing participant perceptions. Refer to the PRO completion guidelines for instructions on the administration of PROs.

All clinician-rated scales must be completed prior to administration of esketamine nasal spray.

Actual dates of PRO and clinician-rated assessments will be recorded in the source documentation and eCRF.

Urine pregnancy tests (at site/local) will be performed in accordance with the Schedule of Activities (Section 1.2) and Section 8.2.4, Pregnancy Testing. Counseling on pregnancy prevention will be provided at all visits, when applicable.

The total blood volume to be collected from each participant will be approximately 30 mL (approximately 7-8 mL/visit), which may vary based on length of participation and local laboratory requirements. Repeat or unscheduled samples may be taken for safety reasons or for technical issues with the samples.

Sample Collection and Handling

The actual dates of sample collection must be recorded in the eCRF.

Refer to the Schedule of Activities (Section 1.2) for the timing and frequency of all sample collections.

Study-Specific Materials

The investigator will be provided with the following supplies:

- Investigator's Brochure for esketamine
- Investigational Product Binder, including the investigational product procedures manual
- Instructions for use documents (participant and healthcare provider versions) for esketamine nasal spray
- Instructions for product quality complaint (PQC) reporting requirements
- Paper versions of PRO questionnaires and PRO completion guidelines
- Paper versions of clinician-administered assessments (MADRS, C-SSRS)
- Rater qualifications/requirements for select clinician-administered assessments
- Electronic devices and associated materials, as applicable
- IWRS Manual
- Sample ICF
- Independent Ethics Committee (IEC)/Institutional Review Board (IRB) approved participant materials

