Any clinically significant abnormalities persisting at the end of the study/early withdrawal will be followed by the investigator until resolution or until a clinically stable condition is reached.

The study will include the following evaluations of safety and tolerability according to the time points provided in the Schedule of Activities in Section 1.2.

The sponsor will use the safety assessments, including clinical laboratory tests, from Week 32 in Study TRD3013 in the database for Day 1 in this long-term extension study; these procedures do not need to be repeated for participants who return for esketamine nasal spray dosing within 14 days after the Week 32 visit in TRD3013.

CONFIDENTIAL – FOIA Exemptions Apply in U.S.

8.2.1. **Physical Examinations**

Body Weight

Body weight will be measured as per the Schedule of Activities.

Nasal Examinations

Nasal examinations (including the upper respiratory tract/throat) will be conducted by a qualified healthcare practitioner authorized by local regulation to conduct a physical examination. The objective of the examination is to rule out any participants with medical conditions that may impede drug delivery or absorption. Abnormalities noted during the nasal examination will be reported as adverse events.

The nasal examination consists of a visual inspection of the nostrils, nasal mucosa, and throat for nasal erythema, rhinorrhea, rhinitis, capillary/blood vessel disruption, and epistaxis, and will be graded as follows: absent, mild, moderate, or severe.

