8.2.2. Vital Signs

Pulse/heart rate, respiratory rate, and blood pressure will be assessed.

Blood pressure and pulse/heart rate measurements will be assessed supine with a completely automated device or using manual techniques.

Blood pressure and pulse/heart rate measurements should be preceded by at least 5 minutes of rest in a quiet setting without distractions (eg, television, cell phones).

8.2.3. **Clinical Safety Laboratory Assessments**

Blood samples for serum chemistry and hematology and a random urine sample for urinalysis will be collected at the time points identified in the Schedule of Activities and as noted in Appendix 8, Clinical Laboratory Tests. Participants should fast for at least 8 hours prior to visits when blood samples will be collected. The investigator must review the laboratory results, document this review, and record any clinically relevant changes occurring during the study in the AE section of the eCRF. The laboratory reports must be filed with the source documents.

8.2.4. **Pregnancy Testing**

A negative urine pregnancy test must be obtained before the first dose of study intervention on Day 1. Additional serum or urine pregnancy tests may be performed, as determined necessary by the investigator or required by local regulation, to establish the absence of pregnancy at any time during the participation in the study and

- every 4 weeks.
- at end of study intervention.
- at 2 weeks after the last dose of study intervention.

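### The schedule and its no-repeat rule leave out the Day 1 pregnancy test that criterion 5 requires of women whose first dose falls after the TRD3013 Week 32 visit

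*Protocol*

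**What the plan says.** Two places in the protocol make the test compulsory. Criterion 5 in Section 5.1 states that "a woman of childbearing potential must have a negative urine pregnancy test on Day 1". Section 8.2.4 adds: "A negative urine pregnancy test must be obtained before the first dose of study intervention on Day 1".

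Day 1 need not be the day of the TRD3013 Week 32 visit. Section 5.5 admits participants who "receive their first dose of esketamine nasal spray within 14 days after the Week 32 visit date in Study TRD3013", and in that case Day 1 is the dosing day.

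The Schedule of Activities (Section 1.3) marks pregnancy testing every 4 weeks, at Week 104/end-of-study/early withdrawal, and at safety follow-up. It has no mark on Day 1.

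A carry-over rule appears twice. Section 8.2 says: "The sponsor will use the safety assessments, including clinical laboratory tests, from Week 32 in Study TRD3013 in the database for Day 1". Footnote a of the schedule says the same and adds that "these procedures do not need to be repeated for participants who return for esketamine nasal spray dosing within 14 days" of the Week 32 visit. Neither statement excepts the pregnancy test.

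Section 8 refers sites to both sources: "Urine pregnancy tests (at site/local) will be performed in accordance with the Schedule of Activities (Section 1.2) and Section 8.2.4, Pregnancy Testing".

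**The concern.** The schedule is what a site coordinator works from day to day. Its pregnancy-testing row looks like the rows whose Day 1 values come from TRD3013 Week 32, and the rule that excuses those repeats does not say that the pregnancy test is different. For a woman of childbearing potential who enters some days after Week 32, that combination can lead to a first dose without the test that determines her eligibility.

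What is at stake is a missed chance to find a pregnancy before esketamine is restarted. Protocol 2.2.2 concludes that use in pregnancy is not recommended, and exclusion 5 bars pregnant women. The next test marked in the schedule is at the first 4-weekly visit. No endpoint, estimand or analysis is involved.

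**Working it through.** The plan gives no figure on this point, so the check is mainly a comparison of texts.

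**1. How the schedule marks Day 1.** The relevant rows of Protocol 1.3, read by column:

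| Row | Day 1 | Dosing visits | Every 4 weeks | Every 24 weeks | Week 104 / end / early withdrawal | Follow-up |
|---|---|---|---|---|---|---|
| Eligibility criteria | X | | | | | |
| Nasal examination, predose | X | X | | | X (if dosed) | |
| Vital signs, pre- and postdose | X | X | | | X (if dosed) | |
| PHQ-9, EQ-5D-5L, MADRS, CGI-S, C-SSRS | | | X | | X | |
| Laboratory tests | | | | X | X | X |
| Pregnancy testing | | | X | | X | X |

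The neighbouring rows fall in sensible columns, so the empty cell is unlikely to be a fault of text extraction. The nasal examination and vital signs, which must be done on Day 1, are marked there. The scales and laboratory tests, which footnote a takes from Week 32, are not. Pregnancy testing is laid out like the second group. The schedule's footnote on pregnancy testing adds no Day 1 test; it only permits extra tests.

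**2. Whether the no-repeat rule reaches the pregnancy test.** The rule covers Week 32 safety assessments and expressly includes clinical laboratory tests. Appendix 8 lists the urine pregnancy test in its table of required safety laboratory assessments. On its wording the rule therefore reaches the test, and nothing takes it out.

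**3. Which rule was intended.** Where Week 32 data are enough for eligibility, the protocol says so: exclusion 4 names the C-SSRS from the Week 32 visit. Criterion 5 names Day 1. The schedule and the carry-over rule therefore need correcting, not the criterion.

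**4. How old a carried-over result could be.** Let d be the number of days from the Week 32 visit to the first dose; the protocol allows d from 0 to 14.

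- d = 0 with a Week 32 test: the result is 0 days old, and one test meets both rules.
- d = 14 with a Week 32 test: the result is 14 days old at first dose, against 0 required.
- No Week 32 test: there is nothing to carry over, and no age can be computed. The documents do not show whether TRD3013 tested at Week 32.

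**5. Order of magnitude per woman.** Assume a negative Week 32 test and a constant pregnancy rate at the ceiling in criterion 6 (under 1% per year with correct, consistent contraception). The chance that a pregnancy becomes detectable within 14 days is then below 0.01 × 14/365 = 0.00038, or about 0.04%. No esketamine is given between the Week 32 visit and Day 1, so the delay itself adds no exposure.

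**The case against.** The strongest reply is that this is one missing mark and not a contradiction. The no-repeat wording is permissive, whereas criterion 5 and 8.2.4 are mandatory, so a site satisfies every instruction by testing. Section 8 points to 8.2.4 as well as to the schedule, the eligibility row is marked on Day 1, and Section 5 forbids waivers. All of this stands. A reader might infer that the protocol permits dosing without the test; it does not.

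A second reply concerns scope. It is tempting to argue that pregnancy testing is carried over simply because Section 4.1 says "Safety assessments include the monitoring of AEs, measurement of body weight, vital sign measurements, clinical laboratory tests, and pregnancy testing", with a matching sentence in the synopsis. That argument fails: the same list contains vital signs and adverse-event monitoring, both still marked on Day 1, so the list cannot define what Week 32 replaces. The narrower route through laboratory tests and Appendix 8 does hold.

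Third, the harm is uncertain. Same-day entry is the default, the number of late-entering women of childbearing potential is not stated, and a Week 32 test is only assumed. This is right, and it limits the size of the point.

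Fourth, enrolment has probably ended: SAP 1.2 describes TRD3013 in the past tense and cites its 2023 report, and SAP version 2 is dated September 2024. That is an inference, but a strong one, and it bears on which fix is still useful.

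What the replies do not remove is that the schedule and footnote a, followed as written, would skip an eligibility test that cannot be waived.

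**Conclusion.** The point holds as a minor safety-consistency error. Criterion 5 and 8.2.4 govern, and a careful site would test. The schedule row lacks the Day 1 mark they call for, and the no-repeat rule in footnote a and 8.2 does not except the test.

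Only women of childbearing potential whose first dose falls after the Week 32 visit are affected. For them, a site relying on the schedule could use a result up to 14 days old, or have none. Same-day entrants with a Week 32 test are unaffected. The conclusion rests on the text alone; the 14-day figure further assumes that a Week 32 test was done. The documents give no count of the women affected and no evidence that any test was missed. A reader should not infer that pregnant women were dosed, or that any safety or efficacy result is in doubt.

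**What to change.** **If enrolment is open:**

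- Mark Day 1 (predose) in the schedule's pregnancy-testing row.
- State in footnote a and in Section 8.2 that the no-repeat rule does not cover the Day 1 urine pregnancy test when Day 1 is later than the TRD3013 Week 32 visit.

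The cost is one mark and one clause in two places, with no test beyond what criterion 5 already requires.

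**If enrolment is closed:**

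- Among the late entrants, whom SAP 5.1.1 already plans to count, identify the women of childbearing potential.
- Compare the date of each woman's pregnancy test with her first-dose date. Use the first-dose date because SAP 1.2 also allows the consent date to serve as Day 1.
- Record any omission as a protocol deviation under the existing process in SAP Appendix 4, before database lock.

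The cost is a date check on a limited group, with no change to any planned analysis.
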